# 7.4. Open-Label Extension for Continued Crinecerfont Access (Month 12 [Week 52] Onwards)

At Month 12 (Week 52), the subject's parent(s) or legal guardian(s) (or the subject, if the subject has reached the age of majority) will review applicable portions of the informed consent form (ICF) and the subject will review applicable portions of the assent form (if applicable) and confirm whether the subject will participate in the optional OLE.

During the OLE, subjects will continue to receive crinecerfont at the appropriate dose based on their body weight at each study visit (25 mg bid if weight is 10 to <20 kg, 50 mg bid if weight is 20 to <55 kg, 100 mg bid if weight is  $\geq$ 55 kg), unless the subject has inadequate efficacy (in the opinion of the investigator), in which case the crinecerfont dose can be increased by doubling the evening dose. Dose can be increased for inadequate efficacy once at the specified weight-based dose (eg, 50 mg BID can be increased to 50 mg gam and 100 mg gpm) but not further unless the subject crosses into the next weight category. If the investigator assesses the subject as having inadequate efficacy and in addition the subject has crossed into the next weight category, the crinecerfont dose should be increased first based on weight (not doubling the evening dose), and then dose adjustment for inadequate efficacy should be assessed at the next scheduled study visit. If the crinecerfont dose is increased due to inadequate efficacy, a follow-up study visit should be performed approximately 1 month after the dose increase for efficacy, PK, and safety assessments. This follow-up study visit is not required for subjects who increase their dose due to crossing into the next weight category. Changes to the crinecerfont dose (whether based on crossing into the next weight category or based on inadequate efficacy) should generally only be made at scheduled study visits. Further guidance on changes to crinecerfont dosing in the OLE is provided in Appendix B.

At Month 12, subjects taking crinecerfont 50 mg bid or higher may elect to switch the crinecerfont formulation (oral solution or capsule) based on preference, eg, if the subject was receiving crinecerfont 50 mg bid oral solution from Week 28 to Month 12 but prefers the capsule, they could switch to 50 mg bid capsule if remaining in the same weight category. Once this formulation preference is established at Month 12, the formulation should remain the same for the rest of the OLE (unless there is a tolerability issue, in which case the subject can revert back to the previous formulation, ideally within approximately 1 month).

During the OLE, subjects will have their glucocorticoid doses adjusted as appropriate and tolerated to achieve the lowest glucocorticoid dose that maintains adequate disease control (in the opinion of the investigator). The glucocorticoid dose reduction will not require dose

reduction below 8 mg/m²/day hydrocortisone equivalents. After each glucocorticoid dose reduction, the investigator should contact the subject/guardian (within 2 weeks) to assess how the subject is tolerating the glucocorticoid dose reduction. In the setting of inadequate disease control, if the glucocorticoid dose is at or above the target, an increase in the glucocorticoid dose should generally be considered only after the crinecerfont dose has been maximized for the subject. Changes to the glucocorticoid and crinecerfont doses should generally be separated by at least 1 month in order to assess the effect of each change.

Starting at Month 12, study visits during the OLE will occur every 6 months. At each OLE study visit (including visits performed approximately 1 month after a dose increase for inadequate efficacy), subjects should hold their morning glucocorticoid and study drug dose until after the predose blood samples are collected, with dosing to occur between approximately 0800 and 0830 hours with breakfast. At Month 24 and every 12 months thereafter, for subjects ≥6 years of age with a body weight ≥20 kg, another blood sample will be collected approximately 3 hours after the morning glucocorticoid and crinecerfont dose. In addition, for all subjects, salivary samples will be collected over the course of the day at Month 24, every 12 months thereafter, and at the early termination visit: at approximately 0600 hours, at approximately 0800 hours prior to morning glucocorticoid and study drug dosing and 3 and 6 hours after dosing, and within 30 minutes prior to the evening dose of glucocorticoid (if subject is not taking evening glucocorticoid dose, then prior to bedtime). Any midday glucocorticoid dose that the subject is receiving should be taken after the 6-hour postdose salivary sample is collected.

The study will continue, and subjects have the option to remain in the OLE until crinecerfont becomes commercially available, the Sponsor elects to discontinue development of crinecerfont for CAH, or the Sponsor elects to discontinue the study.

[figure not shown]
## 7.5. Follow-up Period

A final posttreatment visit will be conducted approximately 4 weeks after a subject's final dose of study drug. This visit is not required if the subject transitions from the open-label treatment period to the OLE or if the subject transitions from the OLE to commercially available crinecerfont or to another crinecerfont study.

## 7.6. Study Schematic

A schematic of the study design for the double-blind, placebo-controlled and open-label treatment periods is shown in Figure 1, and a schematic of the OLE is shown in Figure 2.

Figure 1: Study Schematic for the Double-Blind, Placebo-Controlled Treatment Period and the Open-Label Treatment Period

ET=early termination; GC=glucocorticoid.

<sup>a If needed, the investigator will contact the subject/guardian once laboratory results are available in order to instruct the subject/guardian on any glucocorticoid dose changes and arrange any needed follow-up.

<sup>b At home or the study site. At Week 16 and Week 40, at home is an option if height is not required.

[figure not shown]
<sup>c These visits will occur only if there was any preceding glucocorticoid dose modification during the same treatment period.

<sup>d Subjects will have further glucocorticoid dose adjustment starting at Week 32 only if their Week 32 glucocorticoid dose is >11 mg/m²/day.

<sup>e Glucocorticoid dose adjustments can occur in as few as 1 or up to 3 or 4 steps, depending on the starting and target glucocorticoid doses and the amount of dose adjustment at each step.

f Subjects who complete the Week 52 visit and do not enter the OLE will undergo a safety follow-up visit approximately 4 weeks after the last dose of study drug.

Figure 2: Study Design Schematic for Optional Open-Label Extension for Continued Access to Crinecerfont (Month 12/Week 52 Onwards)

bid=twice daily; FU=follow-up; GC=glucocorticoid; ICF=informed consent form; OLE=open-label extension; qam=in the morning; qpm=in the evening

<sup>a At Month 12 (Week 52) only, the subject's parent(s) or legal guardian(s) (or the subject, if the subject has reached the age of majority) will review applicable portions of the ICF and the subject will review applicable portions of the assent form (if applicable) and confirm whether the subject will participate in the optional OLE At Month 12, subjects taking crinecerfont 50 mg bid or higher may elect to switch the crinecerfont formulation (oral solution or capsule) based on preference.

<sup>b These visits will only occur if the evening dose was doubled at the preceding visit due to inadequate inefficacy.

<sup>c This visit is not required if the subject transitions during the OLE to commercially available crinecerfont or to another crinecerfont study.

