From Week 4 until Week 28, the subject's glucocorticoid dose should be adjusted according to their A4 levels, with the goal to reach a target dose of 8 to 10 mg/m²/day (in hydrocortisone dose equivalents adjusted for body surface area [BSA]) at Week 28, while A4 is controlled, ie, ≤120% of the baseline value or ≤ upper limit of normal (ULN), according to sex and either age (for Tanner stage 1) or pubertal stage (for Tanner stages 2 to 5). The calculation of glucocorticoid dose in hydrocortisone equivalents adjusted for BSA at Day 1 and Week 28 will be based on height and weight measurement at Day 1 and Week 28, respectively. BSA will be updated at Week 16 if height measurement is obtained at Week 16.

Glucocorticoid dose adjustments can occur in as few as 1 or up to 4 steps, depending on the starting and target glucocorticoid doses and the amount of dose adjustment at each step. Reductions in the glucocorticoid dose should follow the guideline of first reducing the most nonphysiologic glucocorticoid type and timing. The target glucocorticoid dose should be within the range of 8 to 10 mg/m²/day while A4 levels are controlled and as long as there is no evidence of glucocorticoid insufficiency. The dose could be lower than this range if the investigator considers this appropriate depending on practical issues considered in clinical practice related to available dosage strengths but will not be mandated to be lower than this range. Before any glucocorticoid dose reduction is implemented, the investigator will evaluate the subject for any symptoms suggestive of glucocorticoid insufficiency using a standardized checklist and will arrange for follow-up if needed after the dose reduction.

The first glucocorticoid dose adjustment step at approximately Week 6 (or when the Week 4 lab results are available) should be guided by the change in A4 at Week 4 from baseline. A

suggested guideline is provided in Table 3, but the exact amount adjusted may differ from this guideline based on practical issues considered in clinical practice related to available dosage strengths. The investigator should contact the subject/guardian once the Week 4 lab results are available in order to provide guidance on the amount of the first glucocorticoid dose adjustment.

Table 3: Guide for Glucocorticoid Dose Adjustments During the Randomized, Placebo-Controlled Treatment Period

Percent Change From Baseline in Serum Androstenedione	Androstenedione Level	Glucocorticoid Dose Adjustment

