# 7.3. Open-Label Treatment Period (Week 28 to Week 52)

From the evening of the Week 28 visit (after all Week 28 assessments have been performed) until the morning of the Week 52 visit, all subjects will receive active study drug based on their Week 28 weight (crinecerfont; 25 mg bid via oral solution for subjects 10 to <20 kg, 50 mg bid via oral solution for subjects 20 to <55 kg, or 100 mg bid via oral capsules for subjects ≥55 kg) with breakfast and evening meals. Subjects and investigators will remain blinded to subjects' randomized treatment group assignment during the entire study. From Week 28 until Week 32, subjects should maintain a stable glucocorticoid regimen to the extent possible, except for stress dosing if needed for illness or other significant physical stress. A blood sample will be collected at Week 32 (at home or the study site).

For subjects who are on >11 mg/m²/day glucocorticoid dose (in hydrocortisone dose equivalents adjusted for BSA [based on weight and height at Week 28]) at Week 32, further adjustments in glucocorticoid dose should be made following guidelines similar to that used during the placebo-controlled period with the goal to reach a target dose of 8 to 10 mg/m²/day in hydrocortisone dose equivalents adjusted for BSA at Week 52, while A4 is controlled. The calculation of glucocorticoid dose in hydrocortisone equivalents adjusted for BSA at Week 52 will be based on height and weight measurement at Week 52. BSA will be updated at Week 40 if height measurement is obtained at Week 40.

The first glucocorticoid dose adjustment step during this period (if done) should be guided by the serum A4 change at Week 32 (compared with Week 28), after the subject has been on open-label active study drug as well as stable glucocorticoid regimen (to the extent possible) for 4 weeks. A suggested guideline is provided in Table 5 but the exact amount adjusted may differ from this guideline based on practical issues considered in clinical practice related to available dosage strengths. The investigator should contact the subject/guardian once the Week 32 lab results are available in order to provide guidance on the amount of the first glucocorticoid dose adjustment (if needed) during the open-label treatment period.

Table 5: Guide for Glucocorticoid Dose Adjustment During the Open-Label Treatment Period

Percent Change from Week 28 in Serum Androstenedione	Androstenedione Level	Glucocorticoid Dose Adjustment

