Any increase	>ULN	Consider whether glucocorticoid dose needs to be increased
Any increase	≤ULN	Maintain current glucocorticoid dose
No change a	Any	Maintain current glucocorticoid dose
Decrease of ≤20%	Any	1 to 2 mg/m²/day glucocorticoid dose reduction
Decrease of >20% to ≤40%	Any	2 to 3 mg/m²/day glucocorticoid dose reduction
Decrease of >40%	Any	3 to 4 mg/m²/day glucocorticoid dose reduction

ULN =upper limit of normal

If the glucocorticoid dose is modified at approximately Week 34, a follow-up blood test (with salivary sample collection) should be arranged approximately 2 weeks later at Week 36 (at home or the study site).

If needed, subsequent glucocorticoid dose adjustments should occur at approximately Week 38 and Week 42 (or when lab results are available) with follow-up blood and salivary tests at Week 40 (at home or the study site) and Week 44 (at home or the study site, if the glucocorticoid dose was previously modified during the open-label treatment period) (Table 6). The target amount of glucocorticoid dose reduction at each step is approximately 1 to 4 mg/m²/day but should be guided by the A4 level at the preceding blood test as well as practical issues considered in clinical practice related to available dosage strengths.

Table 6: Schedule for Blood Tests and Potential Glucocorticoid Dose Adjustments
During the Open-Label Treatment Period

Blood Test (Including Androstenedione)	Glucocorticoid Dose Adjustment Step
Week 36 (at home or the study site)	Potential GC dose adjustment (if needed) at approximately Week 38 (or when Week 36 androstenedione result is available)
Week 40 (at home or the study site)	Potential GC dose adjustment (if needed) at approximately Week 42 (or when Week 40 androstenedione result is available)
Week 44 (at home or the study site)	Potential GC dose increase (if needed) at approximately Week 46 (or when Week 44 labs available) to maintain androstenedione control

GC=glucocorticoid; ULN=upper limit of normal

At all visits, if A4 is >120% of baseline and >ULN, increase glucocorticoid dose as appropriate in order to maintain A4 control.

<sup>a Within reasonable variability in the opinion of the investigator.

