#### Neurocrine Biosciences, Inc., Study No. NBI-74788-CAH2006 Clinical Protocol Amendment No. 3 Final Version

- a The screening period can be extended by up to 4 weeks after discussion with and approval of the Medical Monitor to allow for delayed screening laboratory results that are needed to determine eligibility or to accommodate other extenuating logistical issues, such as scheduling. The Week 4 visit will have a visit window of ±5 days, and subsequent visits through Week 52 will have a visit window of ±7 days. The Week 56 visit (if applicable) visit has a visit window of +7 days. All Week 28 assessments should be completed before a subject begins open-label treatment. Not all assessments must be conducted on the same day, but all assessments for a given visit must be completed within the visit window. If a subject's GC regimen is adjusted due to stress dosing, the subject should resume their GC dosing regimen for at least 3 days before their next scheduled lab test if the duration of stress dosing is 3 days or less, and for at least 7 days before their next scheduled lab test if the duration of stress dosing is ≥4 days (this 3- or 7-day window supersedes all other visit windows).
- b At home or the study site. At Week 16 and Week 40, at home is an option if height is not required. During the screening period, blood and urine collection may be arranged at home.
- c Only if a preceding GC dose adjustment occurred.
- d Subjects will have further GC adjustment starting at Week 32 only if their Week 32 GC dose is >11 mg/m^2/day.
- c For subjects who discontinue the study prior to Week 52, assessments will be performed at the ET visit and at the safety follow-up visit, consisting of the same procedures as shown for Week 56 in the schedule of assessments. A safety follow-up visit is not required if the last dose of study drug was at least 4 weeks prior to the ET visit. Subjects who complete the Week 52 visit and elect to not enter the OLE will undergo a safety follow-up visit approximately 4 weeks after last dose of study drug.
- f Only for subjects age ≥12 years of age.
- Tanner stage at screening and Day 1. Historical assessment of Tanner staging is acceptable if Tanner stage 5 has been previously documented. Tanner staging at subsequent visits is required only if baseline Tanner stage <5. In addition, subjects with Tanner stage 4 at baseline do not need to undergo Tanner staging at Week 16 or Week 40.

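### Open-label glucocorticoid rules conflict for children at or below 11 mg/m²/day whose A4 is both >120% of baseline and >ULN, and the Week 36/44 visit condition is stated in two ways

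*Protocol*

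**What the plan says.** **Restriction by dose.** Protocol Section 7.6, Figure 1 footnote d: "Subjects will have further glucocorticoid dose adjustment starting at Week 32 only if their Week 32 glucocorticoid dose is >11 mg/m²/day". Protocol Table 7 footnote d repeats it: "Subjects will have further GC adjustment starting at Week 32 only if their Week 32 GC dose is >11" mg/m²/day.

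**Rule by A4.** The Synopsis (open-label period), Section 7.3 and Section 9.3.2.2 each carry the sentence "At all visits, if A4 is >120% of baseline and >ULN, increase glucocorticoid dose as appropriate in order to maintain A4 control". None of the three attaches a dose threshold to it.

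**Text behind the footnotes.** Section 7.3 opens the titration rule with "For subjects who are on >11 mg/m²/day glucocorticoid dose" at Week 32 and gives its purpose: "with the goal to reach a target dose of 8 to 10 mg/m²/day in hydrocortisone dose equivalents adjusted for BSA at Week 52", provided A4 is controlled. The Synopsis and Section 9.3.2.2 say the same. The word *only* does not appear in this rule; it appears in the footnotes.

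**Week 36 and Week 44 visits.** Figure 1 footnote c ties them to a dose modification within the same treatment period. Section 7.3 makes the same link: Week 36 follows a change at about Week 34, and Week 44 follows a change made in the open-label period. Table 7 footnote c and the headings of Sections 9.8.3.2 and 9.8.3.4 ask only for some preceding adjustment, without saying in which period.

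**The concern.** A site reading the schematic or the schedule of assessments would conclude that a child at 11 mg/m²/day or less at Week 32 has no further glucocorticoid adjustment. A site reading the body text would conclude that the same child's dose is raised, as appropriate, once A4 control is lost. Entry required more than 12 mg/m²/day (Section 8.1, criterion 4), so children at or below 11 by Week 32 are largely those whose dose came down as the trial intended.

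Two things are at stake. The first is consistent handling of a safety-relevant rule across about 40 centres. The second is the meaning of the Week 52 glucocorticoid summaries, which combine dose with A4 control and so depend on which passage a site followed.

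**Working it through.** There is no planned figure to reproduce, so the check is a comparison of passages.

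**Step 1. When does the A4 rule apply?** Sections 7.2 and 9.3.2.1 have the same A4 trigger in the blinded period, and Section 7.2 defines control as A4 ≤120% of baseline **or** ≤ULN. The negation is A4 >120% of baseline **and** >ULN. That is exactly the trigger in the sentence on all visits, so the rule applies precisely when control is lost.

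**Step 2. Does *adjustment* include increases?** In the protocol's usage, yes.
- The open-label guide (Table 5) has a column headed as dose adjustment, with the row "Consider whether glucocorticoid dose needs to be increased".
- Table 6, under its adjustment-step column, lists the step after Week 44 as a possible increase only.
- Table 7's row for potential glucocorticoid adjustment is marked at Weeks 20 and 44, where Tables 4 and 6 list only increases. So in the table that carries footnote d, the word covers increases.

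**Step 3. Cross the two rules.**

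| Week 32 dose | A4 status | Footnote d | Body text | Conflict |
|---|---|---|---|---|
| >11 | controlled | adjustment possible | titrate toward target | no |
| >11 | >120% of baseline and >ULN | adjustment possible | increase as appropriate | no |
| ≤11 | controlled | no adjustment | no adjustment directed | no |
| ≤11 | >120% of baseline and >ULN | no adjustment | increase as appropriate | **yes** |

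Footnote d is keyed to the Week 32 dose, so the last row also covers a child whose loss of control is first seen at Week 40.

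**Step 4. Follow that child through the visit conditions.** Suppose A4 is out of control at Week 32.
- Footnote d with Figure 1 footnote c: no change, hence no Week 36 visit. The next scheduled A4 test is Week 40, 40 − 32 = 8 weeks later.
- Footnote d with Table 7 footnote c: no change, but a reduction before Week 28 could count as the preceding adjustment, so Week 36 may take place.
- Body text with either footnote c: if the dose is increased at about Week 34, Week 36 takes place.

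If the loss is first seen at Week 40, the same split decides whether Week 44 takes place or the next scheduled test is Week 52, 52 − 40 = 12 weeks later.

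**Step 5. Which analyses use these data?** The confirmatory sequence (Protocol 13.6.1.1, SAP 9.1) ends at Week 28, before either rule operates. SAP 4.5 lists the Week 52 percent change in glucocorticoid dose and the achievement of a physiologic dose as exploratory. SAP 10.3 summarises them descriptively, with and without setting the change to zero on loss of control, and defines the responder as ≤11 mg/m²/day with A4 controlled. For the child in the last row, an increase may restore control or may take the dose above 11, while no increase may leave A4 uncontrolled. The recorded dose change and responder status can therefore differ by passage followed.

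**The case against.** The best defence is that footnote d only abbreviates Section 7.3. There the >11 mg/m²/day condition introduces titration toward a target, the text has no *only*, and the A4 sentence follows as a separate rule, so the full text shows the two coexisting. Read literally, the footnote would also bar stress dosing, which Section 7.2 permits at any time and which Table 7 footnote a itself describes as adjusting the regimen. So it cannot be a complete rule for every dose change. Figure 1 footnote a and the Week 32 and Week 40 visit sections (9.8.3.1, 9.8.3.3) also let the investigator instruct on any dose change and arrange needed follow-up, whatever the dose.

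Most of this stands as evidence of what was probably meant, but it does not remove the conflict. The shorthand reading is plausible and stated nowhere. Table 5, the guide for the first step of that titration, itself contains an increase row, so the footnote cannot be confined to reductions by its source. The stress-dosing point shows the footnote is incomplete without telling a site what else is exempt. The visit sections have no dose condition, which puts them on the side of the body text rather than reconciling it with the footnote.

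**Conclusion.** The inconsistency is real and narrow. It is confined to children at or below 11 mg/m²/day at Week 32 whose A4 is both >120% of baseline and >ULN, together with the double wording of the Week 36/44 condition. It rests on the protocol's own use of *adjustment* and on no numerical assumption.

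Stronger conclusions that a reader might draw are not supported:
- **All children at or below 11 get opposite instructions.** Those with A4 at or below either limit are not in conflict.
- **The text compels an increase.** It says the dose is raised as appropriate, and Table 5 only asks the investigator to consider it.
- **Such a child goes without A4 tests at Weeks 36 and 44.** That follows under Figure 1 footnote c but not necessarily under Table 7 footnote c, and sites may arrange added follow-up.
- **Sites have treated children differently.** The documents show a risk of this, not its occurrence.
- **A percentage of affected children can be given.** The documents report neither within-child A4 variability nor the expected open-label A4 level. Any figure would be assumption, and it would have to take both limits into account, not only the 120% one.
- **The trial's main conclusions are at risk.** The Week 4 and Week 28 endpoints are unaffected; the Week 52 dose summaries that could be affected are exploratory and descriptive.

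It still merits correction, because it concerns site instructions on a safety-relevant rule and costs little to settle.

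**What to change.** Reconcile footnote d of Figure 1 and of Table 7 with the all-visits sentence in the Synopsis and Sections 7.3 and 9.3.2.2, so that a single statement says whether the >11 mg/m²/day condition covers increases as well as reductions. State the condition for the Week 36 and Week 44 visits identically in Figure 1 footnote c, Table 7 footnote c, the Synopsis, Sections 7.3 and 9.3.2.2, and the headings of Sections 9.8.3.2 and 9.8.3.4, including whether an adjustment made before Week 28 counts. Which rule is clinically right is for the sponsor to decide and is not proposed here.

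The cost is wording in an amendment or a clarification letter to sites. It needs no additional patients and no change to the confirmatory analysis.
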